3.3 Safety Endpoints

Safety evaluation includes AE monitoring, serious adverse event (SAE) monitoring, AEs of special interest (AESI) monitoring, vital sign measurements, Columbia-Suicide Severity Rating Scale (C-SSRS) assessments, clinical laboratory testing (hematology, chemistry, and urinalysis), and electrocardiogram (ECG).

4.0 Analysis Populations

The following population sets will be used for the analyses.

The screened population will consist of all participants who signed informed consent and received a subject number.

The modified intention-to-treat (mITT) population includes all participants who receive at least 1 dose of atogepant study drug, have an evaluable baseline period of eDiary data, and have at least 1 evaluable postbaseline 4-week period (Weeks 1 to 4, 5 to 8, 9 to 12, 13 to 16, 17 to 20, or 21 to 24) of eDiary data during the open-label treatment period. The mITT population will be used for all efficacy analyses.

The safety population consists of all participants who received at least 1 dose of atogepant study drug. The safety population will be used for all safety analyses.

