- E. Duration of headache lasting 2 hours or longer on a calendar day unless an acute, migraine-specific medication (i.e., triptan or ergot derivative) was used after the start of the headache, in which case no minimum duration will be specified

Health Outcome Measures:

- Change from baseline in Migraine-Specific Quality-of-Life Questionnaire, version 2.1 (MSQ v2.1)
- Change from baseline in Patient Health Questionnaire (PHQ-9)
- Change from baseline in Work Productivity and Activity Impairment Questionnaire:Migraine v2.0 (WPAI:MIGRAINE)
- Patient Satisfaction with Study Medications (PSSM)
- Patient Global Impression of Change (PGIC)
- Change from baseline in Generalized Anxiety Disorder-7 (GAD-7)
- Change from baseline in PROMIS v2.0 Cognitive Function Abilities Short-Form 6a

All efficacy analyses will be performed using the modified intention-to-treat (mITT) population, consisting of participants who receive at least 1 dose of study intervention (atogepant), have an

evaluable baseline period of eDiary data and have at least 1 evaluable postbaseline 4-week period of eDiary data.

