5 STUDY ACTIVITIES

5.1 Eligibility Criteria

- ✓ 1. Must voluntarily give consent, in a manner approved by an Independent Ethics Committee (IEC)/Institutional Review Board (IRB), prior to the initiation of any screening or study-specific procedures.
- ✓ 2. Adult male or female, between 18 and 75 years, inclusive.
- ✓ 3. Must be using a medically acceptable and effective method of birth control during the course of the entire study.
- ✓ 4. At least a 1-year history of CM, with or without aura, consistent with a diagnosis according to International Classification of Headache Disorders 3rd edition (ICHD-3) 2018 and with or without acute medication overuse defined as follows: use of triptans on ≥ 10 days **or** use of ergots on ≥ 10 days **or** use of simple analgesics (i.e., aspirin, nonsteroidal anti-inflammatory drugs [NSAIDs], or acetaminophen) on ≥ 15 days, **or** use of any combination of triptans, ergots or simple analgesics on ≥ 10 days.
- ✓ 5. Participants must be currently treated with BOTOX for CM: treated with ≥ 2 treatment cycles in the 8 months prior to Visit 2 (Day 1) with documentation of payer authorization or written attestation of self-pay to support continued use of BOTOX. Participants should have ability to coordinate standard-of-care BOTOX injections for Visits 2, 5, and 8 (± 7 days) through their primary care physician or another prescribing healthcare provider.
- ✓ 6. Previous administration of BOTOX prior to study entry was between 8 ± 1 week prior to scheduled Screening to ensure BOTOX administration at 12-week intervals and was between 155 U and 200 U divided between 31 to 39 sites across 7 specific head/neck muscle areas (frontalis, corrugator, procerus, occipitalis, temporalis, trapezius, and cervical paraspinal muscle groups), not to include the masseter. Participants must be able to have stability of dose and injection location paradigm during the study.
- ✓ 7. Must have completed at least 20 days of eDiary data collected during the eDiary screening/baseline period and have 8 to 23 (inclusive) migraine days in the eDiary screening/baseline period (refer to Section 4.1). To determine eligibility for participants who completed 20 to 27 days of eDiary data, use the following formula to calculate the prorated number of migraine days: $(\# \text{ Migraine Days} / \# \text{ Diary Days completed}) * 28 = \text{Prorated Migraine Days}$.

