9.0 Efficacy Analyses

9.1 General Considerations

All analyses on efficacy variables will be performed in the mITT population, unless stated otherwise. For monthly endpoints, baseline is defined as assessments during the last 28 days of baseline period. For efficacy endpoints that are assessed at clinical visits,

baseline is defined as the last non-missing efficacy assessment before the first dose of atogepant.

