14.0 COVID-19 Related Analyses

14.1 Efficacy Evaluation

For the endpoints are collected via eDiary, minimal disruption is expected for these endpoints because participants are expected to complete eDiary at home and submit the responses every day.

The health outcome measures will be collected using eTablet as electronic patient reported outcomes (ePRO) at site. To evaluate the missing rate for these efficacy endpoints, the number of participants who missed at least one visit due to COVID-19 will be summarized at each visit in the efficacy analysis population.

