If a participant confirmed no headache in eDiary (Q1 in Today's Diary, Q2 in Yesterday's Additional Diary, or Q2 in 24-Hour Recall of Yesterday's Diary), then the participant will not answer subsequent questions related to headache symptoms, duration, and acute headache medication use by design. Thus, the acute medication use for that diary ('Today,' '24-Hours Recall,' or 'Yesterday's Additional') will be treated as 'No' when deriving acute medication use day. However, the participants will continue to answer subsequent questions related to non-headache symptoms.

The monthly migraine days is defined the total number of recorded migraine days in the eDiary divided by the total number of days with eDiary records during each monthly period and multiplied by 28. For baseline, a minimum of 20 days' eDiary data during the 28 days of eDiary baseline period is required for the migraine days to be evaluable. For each postbaseline 4-week treatment period, a minimum of 14 days' eDiary data during that period is required for the migraine days to be evaluable. If a participant does not have at least 14 days of diary data for a monthly treatment period, the migraine days for that period will be considered as missing. Migraine days will be derived for each participant at baseline and for each postbaseline monthly treatment period (Weeks 1-4, 5-8, 9-12, 13-16, 17-20, 21-24). The same method to derive monthly migraine days will be used to derive monthly headache days, monthly moderate or severe headache days, monthly cumulative hours of headache, monthly acute medication use days, monthly headache free days,

monthly complete migraine symptom-free day, monthly cardinal migraine symptom-free day, monthly day with an individual non-headache symptom.

If a participant confirmed that acute medications were taken and entered medications in the eDiary, then the acute medication use day will be set to 'Yes.' If a participant reports 'Yes' to the intake of allowed medication(s) to treat an acute migraine but does not list any of them in the diary, then the acute medication use days will not be counted in this situation and vice versa.

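### Site-tablet questionnaires are analysed only in participants with at least one evaluable eDiary month, so a treated participant with none loses all questionnaire data

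*SAP*

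**What the plan says.** **Population.** SAP 4.0 admits to mITT those treated participants who "have an evaluable baseline period of eDiary data, and have at least 1 evaluable postbaseline 4-week period" of diary data, and then states: "The mITT population will be used for all efficacy analyses". Protocol 3.2 says the same ("All efficacy analyses will be performed using the modified intention-to-treat (mITT) population"), as does Protocol 7.2. SAP 9.1 leaves room for exceptions ("All analyses on efficacy variables will be performed in the mITT population, unless stated otherwise"), and Protocol 7.3 has a similar clause. SAP 9.3.2 states no exception for the questionnaires.

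**Evaluable month.** For each post-baseline four-week period, SAP Appendix B says that "a minimum of 14 days' eDiary data during that period is required for the migraine days to be evaluable". The baseline needs 20 diary days.

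**Questionnaires.** SAP 3.2 lists MSQ v2.1, PHQ-9, WPAI, PSSM, PGIC, GAD-7 and PROMIS among the efficacy endpoints, so the mITT rule applies to them. On how they are collected, SAP 14.1 says: "The health outcome measures will be collected using eTablet as electronic patient reported outcomes (ePRO) at site". The same section describes the eDiary as completed at home. For endpoints assessed at clinic visits, SAP 9.1 says that "baseline is defined as the last non-missing efficacy assessment before the first dose of atogepant".

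**The concern.** Inclusion in the analysis of one instrument depends on post-baseline adherence to another. The diary condition makes sense for monthly migraine days, which cannot be derived without diary entries. It has no such purpose for a questionnaire completed on a different device, with a baseline that uses no diary data. For PGIC and PSSM, which have no Day 1 assessment in Protocol Appendix D, a diary baseline has even less bearing.

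Observed questionnaire values from a participant without a single evaluable diary month are therefore discarded. This works against two aims of the plan. Protocol 5.6 keeps participants who stop study drug in scheduled visits so as to limit missing data, and Protocol 7.3 bases the repeated-measures model on all observed post-baseline values. At stake are some precision and possible selection in the questionnaire results, in a single-arm open-label study with no comparator to offset it. SAP 5.0 counts mITT members but does not ask why treated participants fall outside the set.

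**Working it through.** **1. The plan's own figures.** SAP 2.4 assumes 75 enrolled and 20% early termination: 75 × 0.80 = 60 completers. The chance of at least one adverse event at 4% incidence is 1 − 0.96^75 = 0.953. The half-width is 1.96 × 7.0 / √60 = 1.77 (1.81 with the t quantile on 59 df). All three reproduce. None depends on the point made here.

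**2. Who is lost.** Six post-baseline months of 28 days give 168 possible diary days.
- A participant with 13 diary days in every month has 6 × 13 = 78 diary days and no evaluable month. That participant is outside mITT, and all six questionnaire visits (Weeks 4 to 24) are dropped.
- A participant with 14 diary days in one month and none afterwards has 14 diary days in total. That participant is inside mITT, and every questionnaire is kept.

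So the rule does not track questionnaire completeness. It also removes only those with no month reaching 14 days.

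**3. The baseline condition.** Entry criterion 7 in Protocol 5.1 already sets the same threshold: "Must have completed at least 20 days of eDiary data collected during the eDiary screening/baseline period". This part of the mITT definition removes almost nobody enrolled.

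**4. First-month leavers.** Protocol Appendix D schedules the first post-baseline questionnaires at Visit 3 (Day 29 ± 3 days). Someone who attends then has had about 25 or more possible diary days. Someone who leaves earlier normally has only Day 1 values, and none for PGIC or PSSM. The loss is confined to a premature-discontinuation visit, or to later visits attended without enough diary entries. SAP 2.2 pairs the premature-discontinuation visit with Visit 8, but the SAP has no rule placing such a value in an analysis week.

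**5. Size.** The documents give no count of treated participants who would fail mITT, so the number k is an assumption, taken from 0 to 8 of 75. Formulas:
- assessments dropped per questionnaire, at most: 6k
- standard error ratio: √(75 / (75 − k))
- shift in a responder proportion when the excluded are added back: (k / 75) × (20% − 60%), with 60% in mITT and 20% in the excluded both assumed

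| k | Share of 75 | Assessments dropped (max.) | SE ratio | Shift (points) |
|---|---|---|---|---|
| 0 | 0% | 0 | 1.000 | 0 |
| 1 | 1.3% | 6 | 1.007 | −0.5 |
| 2 | 2.7% | 12 | 1.014 | −1.1 |
| 4 | 5.3% | 24 | 1.028 | −2.1 |
| 8 | 10.7% | 48 | 1.058 | −4.3 |

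Worked case for k = 8: (67 × 60 + 8 × 20) / 75 = 55.7%, against 60% reported.

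This treats all 75 as observed at one visit. The result at a given visit would depend on who attended. For scale, the 95% half-width of a 60% proportion at n = 75 is 1.96 × √(0.6 × 0.4 / 75) = 0.111, or about 11 points.

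**The case against.** The strongest case for leaving the plan alone has four parts.

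- **One efficacy set is simple and consistent.** Protocol and SAP agree on it, and denominators match across tables. This stands as a reason of convenience, but it does not explain why diary entries should decide the use of questionnaire data.
- **Few people can be affected.** Entry requires demonstrated diary compliance, sites review compliance at each treatment visit, one month of six suffices, and the diary is returned only at Visit 8, so participants who stop drug can still qualify. This stands. Eight participants would be more than half of the 15 early terminations expected (75 × 0.20), so the upper end of the range is pessimistic.
- **Little depends on it.** SAP 3.2 calls all efficacy endpoints exploratory, and the primary objective is safety, analysed in all treated participants. This stands.
- **The loss is visible.** SAP 5.0 tabulates treated and mITT counts. That shows how many are outside mITT, but not why, nor whether they had questionnaire data.

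A reader might infer that questionnaires from poor diary keepers and early leavers in general are thrown away. The documents do not support that: a single evaluable month restores everything, and most first-month leavers have no post-baseline questionnaire to lose. A reader might also infer that PGIC, PSSM and quality-of-life results are biased in a favourable direction. It is plausible that participants who neglect the diary are less satisfied, but nothing in either document links the two.

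**Conclusion.** The mismatch is real but narrow. Under SAP 4.0, with Protocol 3.2 and 7.2, a treated participant with post-baseline questionnaires but no month of 14 or more diary days is excluded from every questionnaire analysis, although neither the questionnaires nor their baseline depend on the diary. Other poor diary keepers are unaffected, and first-month leavers are affected only by the routes in step 4.

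For an assumed 0 to 8 of 75 excluded, the standard error rises by 0% to about 6%. Under the assumed 20% versus 60% response, a PGIC or PSSM proportion shifts by 0 to about 4 points, well inside its own sampling uncertainty. Neither the count nor the contrast comes from the documents. This is a minor improvement to exploratory analyses. It does not affect the safety conclusions or the diary endpoints.

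**What to change.** - In SAP 4.0, 9.1 and 9.3.2, analyse each clinic questionnaire in all treated participants with a baseline value of that questionnaire (where change is analysed) and at least one post-baseline value. For PGIC and PSSM, require only a post-baseline value. Make this the main analysis with mITT as supportive, or at least a sensitivity analysis.
- State how a questionnaire from a premature-discontinuation visit maps to an analysis week. Without this, some of the affected participants would still not be recovered.
- In SAP 5.0, report how many treated participants fail mITT and for what reason.
- Record the change in SAP 15.1, which now states that there are none.
- Leave the diary endpoints, including AIM-D, on mITT.

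**Cost.** SAP wording, a population flag per questionnaire and one additional run. No new data are needed. Denominators will differ slightly between diary and questionnaire tables, and the SAP will depart, with documentation, from the population wording in Protocol 3.2 and 7.2. The new sets still require a post-baseline value, but of the instrument being analysed.

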5.0 Participant Disposition

The total number of participants who were screened, screen failed (i.e., subjects who consented to participate in the study but were not enrolled) and treated will be summarized. A summary of participant accountability by investigator will be provided where the number of participants in each of the following categories will be tabulated:

- Participants enrolled in the study;
- Participants who screen failed;
- Participants who took at least one dose of study treatment;
- Participants who completed study treatment;
- Participants who prematurely discontinued study treatment;
- Participants in the mITT population.

The number and percentage of enrolled participants who completed study treatment and study will be summarized respectively.

6.0 Study Treatment Duration and Compliance

Duration of study drug (atogepant) will be summarized for safety population.

Duration of atogepant treatment is defined for each participant as last dose date minus first dose date + 1. Duration of atogepant treatment will be summarized by BOTOX dose group (≤ 155 units or >155 units) and overall for the safety population using the number

of participants treated, mean, standard deviation, median, Q1, Q3, minimum and maximum. In addition, the number and percentage of participants in each treatment duration of ≥ 1 day, ≥ 28 days, ≥ 56 days, ≥ 84 days, ≥ 90 days, ≥ 112 days, ≥ 140 days, and ≥ 168 days will be summarized.

The number and percentage of participants treated in each BOTOX treatment cycle (Visit 2, Visit 5, and Visit 8) will be summarized by BOTOX dose group (≤ 155 units or >155 units categorized at Visit 2) and overall.

Participant-years of atogepant, defined as exposure to the atogepant treatment in years, will be summarized for the safety population.

Treatment compliance for a specific period is defined as the number of atogepant study medications actually taken during that period divided by the number of study medications that should have been taken during the same period. Percent atogepant treatment compliance as well as the associated compliance categories ($< 80\%$, $80\% - 120\%$, $> 120\%$) will be summarized in each period between 2 consecutive visits, as well as in the entire treatment period from the first dose of the open-label atogepant study drug actually taken to the last dose of open label atogepant study drug actually taken for the safety population.

7.0 Participant Characteristics

Categorical variables will be summarized with the number and percentage of participants; percentages will be calculated based on the number of non-missing observations. Continuous variables will be summarized with descriptive statistics (number of non-missing observations, mean and standard deviation, median, Q1, Q3, minimum and maximum).

7.1 Demographics and Baseline Characteristics

Demographics and baseline characteristics will be summarized for the safety population and mITT population. Disease characteristics will be summarized for the safety population. Unless otherwise specified, baseline is defined as the last non-missing value prior to the first dose of atogepant.

Continuous demographic variables include age, weight, height, and body mass index (BMI).

Categorical demographic variables include:

- Sex
- Ethnicity (Hispanic or Latino, Not Hispanic or Latino)
- Race (White, Black or African American, Asian, American Indian or Alaska Native, and Native Hawaiian or Other Pacific Islander, Multiple)
- Age group (< 20, 20-29, 30-39, 40-49, 50-59, 60-69, ≥ 70 years)
- Age group (< 40 years, 40-64 years, ≥ 65 years)
- Nicotine user (current, former, never, unknown)
- Alcohol user (current, former, never, unknown)
- Actual BOTOX dose received at Visit 2.

Disease characteristics are contained in migraine headache history eCRF, including diagnosis, duration of migraine, duration of chronic migraine, average number of migraine or headache days per month in the last 1 year, duration of BOTOX administration, average number of BOTOX treatment cycles in the last 8 months. Migraine Disorder Duration and Chronic Migraine Disorder Duration will be determined from the earliest diagnosis date recorded as part of the migraine headache history as compared to the date of the subject's screening Visit 1. Duration of Botox Administration for Chronic Migraine will be determined from the date of first Botox administration for Chronic Migraine recorded as part of the migraine headache history as compared to the date of the subject's screening Visit 1.

7.2 Medical History and Prior and Concomitant Medications

Medical history and prior and concomitant medications will be summarized for the safety population.

Medical history data will be coded using the Medical Dictionary for Regulatory Activities (MedDRA). The actual version of the MedDRA coding dictionary will be noted in the statistical tables and clinical study report. The number and percentage of participants in each medical history category (by MedDRA system organ class (SOC) and preferred term (PT)) will be summarized. The SOC will be presented in alphabetical order, and the PTs will be presented in alphabetical order within each SOC. Participants reporting more than one condition/diagnosis will be counted only once in each row (SOC or PT).

Prior and concomitant medications will be summarized by generic names. Concomitant medication will be summarized for the open-label period and follow-up period. A prior medication is defined as any medication taken prior to the date of the first dose of study drug. A concomitant medication is defined as any medication that started prior to the date of the first dose of study drug and continued to be taken after the first dose of study drug or any medication that started on or after the date of the first dose of study drug, but not after the date of the last dose of study drug plus 30 days or Visit 9 which comes later. The number and percentage of participants taking medications will be summarized by generic drug name based on the World Health Organization (WHO) Drug Dictionary for both prior and concomitant medications. The number and percentage of participants taking prior preventive migraine medications will be summarized by generic name and class, and the number and percentage of participants taking prior acute headache medication will be summarized by generic name.

The dose of concomitant BOTOX medication injected will be summarized totaled across the head/neck injection areas and separately for each head/neck injection area. This will be done for each treatment cycle (Visit 2, Visit 5, and Visit 8) and totaled across injection cycles will be summarized by BOTOX dose groups (≤ 155 units or >155 units). The total

volume of concomitant BOTOX medication injected will be summarized by BOTOX dose groups.

7.3 Protocol Deviations

Protocol deviations include eligibility criteria violations, receipt of wrong treatment or incorrect dose of study treatment, development of withdrawal criteria without being withdrawn, and use of prohibited concomitant medications. A listing of participants with protocol deviations will be provided.

For each of the following protocol deviation categories and across all categories, the number and percentage of enrolled participants with at least one protocol deviation will be summarized:

- Participants entered into the study even though did not satisfy entry criteria;
- Participants developed withdrawal criteria during the study but was not withdrawn;
- Participants received wrong treatment or incorrect dose of study treatment;
- Participants took prohibited concomitant medication.

